6.3 Study Objects

6.3.1 Study Completion Condition

The screening subjects and enrolled subjects, as well as the subjects who complete the study will be summarized. The reasons for screening failure and early termination will be classified and summarized.

All the subjects with failed pre-procedure screening will be listed, and the subjects' ID, age,

gender, date of screening failure and the reason for screening failure are explained by study site. All of the subjects with early termination will be listed, and the subjects' ID, age, gender, beginning date, ending date and the duration in the study and the reason for early termination are explained by study site.

6.3.2 Protocol Deviation

Major protocol deviation will be summarized, and the follow-up period and reason for major protocol deviation will be classified and summarized. List of major protocol deviation will also be presented.

6.3.3 Demographic and Baseline Characteristics

The patients' demographic characteristics (age, gender and nationality) are summarized and described. The qualitative indicators are summarized with frequency and percentage, and the quantitative indicators are summarized with descriptive statistics (mean, standard deviation, median, maximum and minimum, Q1 and Q3). The demographic and baseline characteristics need present for all enrolled subjects and ITT population.

The baseline characteristics shown below are analyzed with the descriptive method similar to that used for demographic characteristics:

1) History of fibrillation atrial, including:

- Symptomatic fibrillation atrial history (month) according to the initial PAF symptom or record
- Average duration (hour) per episode within 12 months before enrollment
- Average frequency of episodes (times/month)
- Objective evidence of confirmed fibrillation atrial within 12 months before enrollment: surface electrocardiogram (ECG), 24-hour dynamic electrocardiogram (24 Holter), transtelephonic monitor (TTM) and others
- Presence of fibrillation atrial related symptom
- Fibrillation atrial/ Atrioventricular tachycardia/ auricular flutter (AF/AT/AFL status)
- Paroxysmal or persistent fibrillation atrial related symptom

2) Medical history – underlying heart disease, including:

- Presence of definite organic heart disease
- Type of organic heart disease

- Cardiac function NYHA grading
- Presence of other complications
- Type of other complications
- Presence of thrombotic disease history
- Type of thrombotic disease history
- Presence of hemorrhagic disease
- Presence of diabetes
- Presence of other arrhythmia symptoms
- Type of other arrhythmia disease

3) Echocardiography

- Whether the subject has undergone transesophageal echocardiography (TEE) examination within 24 hours before the procedure
- Presence of atrial thrombosis
- Whether the left atrial diameter has been tested?
- Left atrial diameter (LAD) (cm)
- Whether the subject has undergone trans thoracic echocardiography (TTE) examination?
- Whether the ultrasound cardiography shows left ventricular ejection fraction
- Left ventricular ejection fraction (LVEF) (%) showed with echocardiography

4) Treatment of fibrillation atrial and other heart diseases, including:

- Whether the subject has taken antiarrhythmic drugs within the past 3 months
- Whether the drug has been stopped for 5 half-lives
- Whether the subject has taken anticoagulant drugs within the past 3 months
- Whether the subject has taken other cardiac drugs within the past 3 months
- Whether the subject has received electrical conversion treatment before the procedure due to fibrillation atrial

5) ECG examination, including:

- Heart rhythm
- With or without atrioventricular block
- The grade of atrioventricular block
- Bundle branch block
- The type of bundle branch block

6) 24-hour dynamic electrocardiogram (24 Holter) examination, including:

- Heart rhythm

7) Transtelephonic monitor (TTM), including

- Heart rhythm
- Whether the fibrillation atrial symptom occurs during monitoring

Among the abovementioned characteristics, fibrillation atrial/ atrioventricular tachycardia/auricular flutter, ECG examination, 24-hour dynamic electrocardiogram (24 Holter) examination, and transtelephonic monitoring (TTM) will be described and analyzed together with each follow-up time point. At each follow-up time point, if the AF/AFL/AT arrhythmia recurrence lasts ≥ 30 seconds and is documented by ECG, 24-Holter or TTM, the examination characteristic will be summarized as well.

All the baseline data collected in the CRF will be tabulated and explained.

6.3.4 Concomitant Medication

The cardiac drugs and other drugs used during treatment is described and analyzed. The cardiac drugs will be further classified and described by antiarrhythmic drugs, anticoagulants and other cardiac drugs. The cardiac drugs and other drugs will be coded with World Health Organization drug dictionary (WHODRUG) and Anatomical Therapeutic Chemical classification (ATC), and will be classified, summarized and described with ATC Level IV and Preferred Name, respectively.

Meanwhile, the previous drugs and concomitant drugs will also be described and analyzed, respectively. The previous drugs are defined as the drugs that have been stopped before the beginning of the study. The concomitant drugs are defined as the drugs that are used after the beginning of the study, or those have been used before the study, but are continued after the beginning of the study.

6.4 Ablation Parameters

Descriptive analysis is conducted for ablation procedure parameters, and the procedure parameters include:

- Total X-ray fluoroscopy dose (mGr)
- Intraoperative transcatheter fluid infusion (ml)
- The maximum infusion rate of the intraoperative transcatheter fluid (ml/min)
- Whether the subject has been observed for 30 minutes after CPVI
- Whether isoproterenol has been given to induce fibrillation atrial 30 minutes after CPVI
- Whether other drugs have been given to induce fibrillation atrial 30 minutes after CPVI
- Whether an immediate success has been achieved
- Whether the exit block has been observed
- Presence of linear ablation
- Presence of other ablation
- Whether the sheathing canal has been used during the procedure
- Whether CART03 version 3.2 or later version has been used to mapping the left atrium before radiofrequency ablation
- Whether the VisiTag module has been used
- Whether radiofrequency discharge is conducted
- Average power (watt)
- Average temperature (C)
- CF
- Number of PV reconnection targets
- Procedual time, ablation time and fluoroscopy time
- The longest duration of one-time single discharge (second)
- The maximum decrease in impedance value (ohm)
- Presence of any other types of spontaneous arrhythmia during the procedure

- Presence of any other types of induced arrhythmia during the procedure

6.5 Effectiveness Analysis

6.5.1 Primary Efficacy Endpoint Analysis

ITT population is used for the main analysis of the primary endpoint, and PP population is used for supportive analysis.

The primary endpoint for this study is freedom from documented symptomatic AF, AT, or AFL episodes through 12-months follow-up after the index ablation procedure (includes a 3 months blanking period).

The following will also be considered primary effectiveness failures and will be included in the effectiveness analysis population:

- Acute procedural failure (i.e., failure to confirm entrance block in all pulmonary veins with an isoproterenol intravenous challenge 0.5 h post procedure or use of a non-study catheter to treat the study arrhythmia);
- A repeated ablation after the 90-day blanking period

Atrial tachyarrhythmia recurrence events will be recorded and included in study analysis after a 90-day blanking period. Recurrence during the blanking will not be considered treatment failure.

The number of subjects who achieved this endpoint and its percentage will be presented. A two-sided binomial exact 95% confidence interval will be computed. Superiority against historic control performance goal (50%) after applying THERMOCOOL® SMARTTOUCH™ catheter with contact sensitivity will be claimed if the lower bound of this confidence interval is above 50%.

For the subjects failing to be followed up to the primary endpoint, with conservative consideration, these subjects are considered as primary effectiveness endpoint failure in the main analysis.

Sensitivity analysis will be conducted for the primary endpoints using the methods below:

- For the subjects failed to be followed up to the primary endpoint, the primary endpoint is considered as missing in the analysis, and the subjects will be excluded from ITT analysis set.

A Kaplan-Meier analysis will be performed for the time to the first documented symptomatic AF, AT, or AFL episode. The first quartile, median, third quartile and 95% confidence intervals of the first quartile, median and the third quartile will be computed.

Kaplan-Meier curves for episode time of symptomatic AF, AT or AFL first recorded during 12 months follow-up (Day 91 to 361) after the first ablation will be presented.

Logistic regression method will be used to analyze the effect of baseline variables and procedure parameters on the primary effectiveness endpoint. For the influence factor of episode rate, univariate logistic regression analysis model will be first used for preliminary screening of influence factors, of which, the influence factor with p-value <0.2 will be placed into multiple factor regression model for further analysis; and step-wise regression method will be used for further variable screening, of which, the influence factor with p-value <0.2 will be removed from multiple factor model. Please refer to baseline characteristics in Section 6.3.3.

Repeat ablation beyond the blanking period will be described and summarized.

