8.2 Sample Size and Power Calculation

Assuming the true rate for freedom from documented symptomatic AF, AT, or AFL episodes through 12-months follow-up is about 65% with CF-guided approach and a historic control performance goal of 50%,¹² a sample size of 150 is needed in order to have 95% power to have the lower bound of the two-sided 95% confidence interval of this recurrence free rate above the historic control performance goal. This sample size is computed using nQuery Advisor® version 7.0. Considering 20% dropout rate, a sample size of 188 is needed. This study will enroll approximately 200 subjects (no less than 188).

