8.4.2 Primary Endpoint

The primary effectiveness endpoint for this study will be freedom from documented symptomatic AF, AT, or AFL episodes through 12-months follow-up after the index ablation

procedure (includes a three month blanking period). The number of subjects who achieved this endpoint and its percentage will be presented. A two-sided binomial exact 95% confidence interval will be computed. Superiority against historic control performance goal will be claimed if the lower bound of this confidence interval is above 50%.

A Kaplan-Meier analysis will be performed for the time to the first documented symptomatic AF, AT, or AFL episodes. The first quartile, median, and third quartile for the time to first AF, AT, or AFL episode through 12-months follow-up period will be presented. The 95% confidence intervals for the first quartile, median, and third quartile will be computed.

Baseline covariates and procedure parameters that affect the occurrence of AF, AT, or AFL episodes through 12-months follow-up period will be explored using logistic regression models.

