3.6 Subject Disposition

- **Enrolled Subjects:** patients who sign the informed consent.
- **Excluded Subjects:** subjects that are enrolled but never undergo insertion of the Study Catheter. Excluded subjects will not be evaluated in this study.
- **Discontinued Subjects:** subjects that have the investigational catheter inserted but are not treated with the investigational device (i.e., no RF energy applied). Subjects will be categorized as “discontinued” if ablation was not possible due to non-investigational equipment failure, anatomy reasons or if their arrhythmia was determined at the time of electrophysiological study to be a non-study arrhythmia (e.g., atrial flutter).
- **Lost to Follow-up Subjects:** all subjects should be encouraged to return for protocol required office, clinic visit for evaluation during the study follow-up period. If a subject is unable to return for an office or clinic visit or unable to be contacted by telephone, 3 separate telephone calls should be made to obtain subject related safety information. All attempts should be documented in the source documents. If the subject does not respond to the 3 telephone calls, then the investigator must send a certified letter to the subject. If the subject does not respond to the letter, then the subject will be considered “lost to follow-up” for the current study visit. Subject contact must be attempted at each follow-up time point and if unable to contact the subject after 3 phone calls, the subject should once again be sent a certified letter. Only after failing to contact the subject at the final follow-up visit, the subject will be considered lost to follow-up and the study termination will be recorded in the individual case report form.

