4.2.4 Total procedural time, ablation (RF) time and fluoroscopy time

4.3 Safety Endpoint

The incidence of AEs related with the procedure or study catheter

[figure not shown]

Figure 1: Right/left pulmonary veins was divided into 3, 6, 9 and 12 point position from PV to the atrium

5 Sample Size and Statistical Power

Assuming the true rate for freedom from documented symptomatic AF, AT, or AFL episodes through 12-months follow-up is about 65% using THERMOCOOL® SMARTTOUCHTM catheter with Contact Force Sensing Capability and a historic control performance goal of 50%, a sample size of 150 is needed in order to have 95% power to have the lower bound of the two-sided 95% confidence interval of this free-from-recurrence rate above the historic control performance goal¹. The calculation formula⁵⁴ was refer to the paper written by Xinran Tang.

nQuery Advisor® version 7.0 is used for calculation of this sample size. Assuming the dropout rate of the study is 20%, $150 / (1-0.2) = 188$ subjects is needed in total. About 200 subjects are planned to be enrolled in this study (at least 188 subjects).

6 Data Analysis

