6.2 Analysis Population

6.2.1 Intent-to-treat (ITT) Population

Intent-to-treat (ITT) Population: All enrolled subjects who meet the inclusion/exclusion criteria and have signed informed consent form.

ITT Population will be used for baseline summary and provide analysis for primary efficacy endpoints.

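### The 188-subject sample size assumes dropouts leave the denominator, but the main ITT analysis counts them as failures: at the planned 20% dropout within ITT, exact power is about 7–8%, not 95%

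*SAP*

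**What the plan says.** **Sample size.** Protocol 8.2 assumes that freedom from recurrence "through 12-months follow-up is about 65% with CF-guided approach", against a performance goal of 50%. Both Protocol 8.2 and SAP 5 state that "a sample size of 150 is needed in order to have 95% power". The protocol then says "Considering 20% dropout rate, a sample size of 188 is needed", and SAP 5 shows the division 150/(1 − 0.2) = 188. Planned enrolment is about 200, with a minimum of 188.

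**Success rule.** The interval is the two-sided exact binomial 95% interval. Protocol 8.4.2 says "Superiority against historic control performance goal will be claimed if the lower bound of this confidence interval is above 50" (per cent).

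**Missing outcomes.** SAP 6.5.1 makes ITT the main analysis. For ITT subjects not followed to the primary endpoint, "these subjects are considered as primary effectiveness endpoint failure in the main analysis". In the sensitivity analysis, by contrast, "the primary endpoint is considered as missing in the analysis, and the subjects will be excluded from ITT analysis set". The protocol has no rule for a missing primary endpoint, and SAP 8 records no changes to the protocol's methods.

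**Who is in ITT.** SAP 6.2.1 defines it as "All enrolled subjects who meet the inclusion/exclusion criteria and have signed informed consent form". No follow-up is required. SAP 3.6 says of subjects who never have the catheter inserted: "Excluded subjects will not be evaluated in this study". Neither document defines dropout.

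**The concern.** Dividing by (1 − 0.2) serves one purpose: to leave 150 subjects in the analysis after dropouts have been removed. The main analysis does not remove them. It keeps them and gives each one a failure, so dropout lowers the success rate instead of only shrinking the sample. Enrolling more subjects to offset dropout does not repair this, because the extra subjects drop out at the same rate.

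At the plan's own dropout rate, a catheter that performs exactly as assumed would usually miss its goal. Read against a stated 95% power, that miss would look like good evidence against the catheter.

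**Working it through.** **Inputs.** True freedom 65%, goal 50%, 150 evaluable, 95% power, 20% dropout, 188 to 200 enrolled (Protocol 8.2, SAP 5); exact two-sided 95% interval with lower bound above 50% (Protocol 8.4.2, SAP 6.5.1); dropouts scored as failures (SAP 6.5.1).

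**Formulas.** The critical count r is the smallest number of successes x out of n whose Clopper-Pearson lower bound, the 2.5% quantile of Beta(x, n − x + 1), exceeds 0.5. Power is P(X ≥ r) for X ~ Binomial(n, p).

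**Step 1: reproduce the plan's figure.** With p = 0.65:

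| n | r | Power | One-sided type I error |
|---|---|---|---|
| 150 | 88 | 95.5% | 0.020 |
| 160 | 93 | 97.0% | 0.024 |
| 188 | 108 | 98.7% | 0.024 |
| 200 | 115 | 98.8% | 0.020 |

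The 150 for 95% power is confirmed, and 150/0.8 = 187.5 rounds up to 188. If dropouts leave the denominator, 188 enrolled gives 150 evaluable (95.5%) and 200 gives 160 (97.0%).

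**Step 2: apply the main-analysis rule.** Let d be the share of ITT subjects not followed to the endpoint, independent of outcome. Dividing by (1 − 0.2) treats 65% as the rate among subjects who are followed, so the ITT success rate is p = 0.65 × (1 − d).

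| d | ITT rate | Power, n = 188 (r = 108) | Power, n = 200 (r = 115) |
|---|---|---|---|
| 0% | 65.0% | 98.7% | 98.8% |
| 3% | 63.05% | 95.1% | 95.4% |
| 5% | 61.75% | 90.1% | 90.4% |
| 10% | 58.5% | 64.5% | 64.1% |
| 15% | 55.25% | 29.8% | 28.5% |
| 20% | 52.0% | 7.7% | 6.8% |

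The number of dropouts is treated as random here. With exactly 38 of 188 lost, at least 108 of the 150 followed subjects must succeed, which has probability 4.2%; with 40 of 200, it is 3.9%. With 20% scored as failures, freedom among followed subjects would have to be about 79% to give 95% power. At an ITT rate of 52%, about 8,100 subjects would be needed.

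**Step 3: let part of the 20% leave before ITT.** The 188 counts consented subjects, so some attrition may never enter ITT. The documents give no split; those below are assumptions, with 80% of enrolled subjects evaluable throughout.

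| Points of the 20% leaving before ITT | N = 188: ITT size (r), power | N = 200: ITT size (r), power |
|---|---|---|
| 5 | 179 (104), 19% | 190 (109), 26% |
| 10 | 169 (98), 52% | 180 (104), 53% |
| 15 | 160 (93), 80% | 170 (99), 81% |
| 20 | 150 (88), 95.5% | 160 (93), 97.0% |

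For N = 188, rounding the evaluable number to 150 rather than using 150.4 lowers the first three powers to 18%, 50% and 79%. Power reaches 95% only if all 38 dropouts (N = 188) or at least 38 of 40 (N = 200) leave before ITT. At N = 188, with 37 of 38 leaving, ITT is 151, r steps to 89, and power is about 94%.

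**Step 4: let dropout depend on outcome.** Suppose instead that 65% is the rate over all ITT subjects and a share f of the 20% who drop out would have failed anyway. The ITT success rate is then 0.65 − 0.20 × (1 − f). These shares are also assumptions.

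| f | ITT rate | Power, n = 188 / 200 |
|---|---|---|
| 0.35 (independent) | 52% | 7.7% / 6.8% |
| 0.50 | 55% | 27% / 26% |
| 0.75 | 60% | 79% / 79% |
| 0.90 | 63% | 95% / 95% |

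**The case against.** The strongest reply is that 7–8% is a corner case. It needs all 20% to fall inside ITT and to be unrelated to outcome. Some loss between consent and ITT entry is built in: consent precedes study-specific tests, and a documented left atrial thrombus found shortly before ablation is an exclusion. Dropouts may also fail more often than completers. In addition, SAP 6.5.1 openly calls its rule conservative and prespecifies the completers-only analysis, so a miss would be reported beside a well-powered result.

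The conditions are real, and Steps 3 and 4 show their effect. They do not rescue the stated 95%. With half of the dropout outside ITT, power is about 52%. Informative dropout restores 95% only if about nine in ten dropouts would have failed, and only if 65% is read as the rate in everyone, which the division by 0.8 does not suggest. The completers-only analysis does help interpretation, but it does not carry the superiority claim, and neither do the per-protocol and Kaplan-Meier analyses.

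It is also true that the arithmetic leading to 150 and 188 is correct in itself. The fault is that it belongs to a different analysis from the main one.

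**Conclusion.** The concern holds and must be fixed. The 95% power describes the completers-only sensitivity analysis. For the main ITT analysis at 65% true freedom, power is 7.7% (188 subjects) or 6.8% (200) at the planned 20% dropout, about 64% at half that rate, and 95% only at about 3% or less. These figures rest on three assumptions: dropout occurs within ITT, it is independent of outcome, and 65% is the rate among followed subjects. Relaxing the first or second raises power, but only extreme departures bring it back to 95%. The rule does not inflate the false-positive rate.

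**What to change.** In Protocol 8.2 and SAP 5:

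1. Define dropout as an ITT subject not followed to the primary endpoint. State that a subject with a qualifying failure before withdrawal is already a failure and not a dropout. Give separately the attrition expected between consent and ITT entry, and say whether subjects with no catheter inserted (SAP 3.6) count in ITT.
2. Replace the claim of 95% power for 188 subjects with 20% dropout by exact power under the failure rule: about 95% at 3% dropout, 90% at 5%, 64% at 10%, 29–30% at 15%, and 7–8% at 20%.
3. State that the 95% figure (95.5% with 150 evaluable, 97.0% with 160) applies to the completers-only sensitivity analysis.

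Keep dropout-as-failure as the main analysis. Since the protocol has no missing-outcome rule, state the rule in Protocol 8.4.2 as well, or record it in SAP 8.

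Optionally, before endpoint data are reviewed, add to the planned Kaplan-Meier analysis the 12-month freedom estimate with its two-sided 95% lower bound against 50%, labelled as a sensitivity analysis. Acute procedural failures and post-blanking repeat ablations would count as events. Subjects event-free at an in-window visit on Days 330–359 would be carried as event-free to Day 360, which credits up to 30 unobserved days and must be aligned with the Day 91 to 361 span in SAP 6.5.1. This addition assumes non-informative censoring.

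The cost is text and a short table. Patient numbers, the primary rule and type I error do not change. The protocol correction is an amendment under Protocol 9.4.4: ethics approval if substantial, otherwise notification. The drawback is a less favourable power statement, and the correction discloses the false-negative risk without removing it.

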6.1 General Principle

All statistical procedures will be completed using SAS version 9.2 or later version. Statistical methods applied will be mostly descriptive statistics.

The continuous variables will be summarized by the statistics listed in table 2:

Table 2: Descriptive statistics of quantitative measures

Statistics	Decimal place preserved
N (Total number of patients in treatment group)	0

Confidential

n (Number of patients without missing values)	0
Mean, median, Q1, Q3	Preserve one more decimal place than the original data, up to no more than four decimal places
Standard deviation	Preserve two more decimal place than the original data, up to no more than four decimal places
Maximum, minimum	Preserve the same decimal place as the original data, up to no more than four decimal places

The categorical variables will be summarized with the frequency and percentage of each type. The missing value will not be included in the calculation of percentage, unless otherwise specified.

Kaplan-Meier method will be used for the time to onset of the first symptomatic AF, AT, or AFL episode. The statistics listed in Table 3 will be used to describe the results of statistical analysis model.

Table 3: Statistics of statistical analysis model

Statistics	Decimal place preserved
Q1, Q3, median	Preserve one more decimal place than the original data, up to no more than four decimal places
95% confidence interval	Preserve two more decimal place than the original data, up to no more than four decimal places
P-value	Usually preserve 3 decimal places (or <0.001, or >0.999)

Hypothesis testing will be carried out at the two-sided $\alpha=0.05$ level unless otherwise specified, and 2-sided 95% confidence intervals will be presented.

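### The only missing-data sensitivity analysis deletes event-free dropouts and so understates the 12-month success rate; the 12-month Kaplan-Meier rate is not requested

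*SAP*

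**What the plan says.** SAP 6.5.1 uses the ITT population for the main analysis of the primary endpoint. "A two-sided binomial exact 95% confidence interval will be computed", and superiority is claimed if its lower bound exceeds 50%. Subjects not followed to the primary endpoint count as failures.

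One sensitivity method is listed for these same subjects: "the primary endpoint is considered as missing in the analysis, and the subjects will be excluded from ITT analysis set". The section does not say whether someone who recurs and later leaves belongs to this group.

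The same section adds: "A Kaplan-Meier analysis will be performed for the time to the first documented symptomatic AF, AT, or AFL episode". The output requested is the quartiles with their confidence intervals and a curve over Days 91 to 361. No estimate at 12 months is requested, and no imputation or tipping-point analysis is listed. Protocol 8.4.1 leaves data handling rules to the SAP, but SAP section 9 (Data processing principle) contains none.

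Protocol 8.2 supplies the planning figures: "a sample size of 150 is needed in order to have 95% power", for a true rate of 65% against a goal of 50%, and "Considering 20% dropout rate, a sample size of 188 is needed". SAP section 5 repeats them.

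**The concern.** Failures and successes become known at different times. A recurrence at month 5 settles the outcome at month 5, whereas freedom from recurrence is settled only at the 12-month visit. If subjects without a settled outcome are removed, some would-be failures stay in because they failed before they could leave, while every would-be success who leaves is removed. The remaining sample holds too many failures.

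This matters because the main rate is itself depressed by dropout: at 65% true success and 20% dropout it is expected to be 0.65 × 0.80 = 52%. A reader who wants the actual 12-month rate has only the deletion analysis to turn to, and that does not estimate it either.

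The planned Kaplan-Meier output does not fill the gap. If about 65% stay free of recurrence, the median and third quartile are never reached, so only the first quartile can be estimated. Its event is also narrower than primary failure, which includes acute procedural failure and repeat ablation after blanking.

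**Working it through.** **Inputs from the documents.** True rate 65%, goal 50%, 150 evaluable subjects, 95% power, 20% dropout (Protocol 8.2; SAP section 5). Exact two-sided 95% interval with lower bound above 50% (SAP 6.5.1). 90-day blanking period (SAP 4.1).

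**Assumptions not in the documents.** Recurrences spread over Days 91-360; the timing of dropout; in step 4, the leaving rates.

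**1. The plan's own figure.** With n = 150, the exact lower bound exceeds 50% from 88 successes upward (88/150: 50.3%; 87/150: 49.7%). P(X ≥ 88 | n = 150, p = 0.65) = 95.5%, and 150/0.8 = 187.5, rounded up to 188. The plan's figures reproduce.

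**2. Natural reading: observed failures kept, event-free dropouts deleted.** Let d be the dropout proportion, unrelated to outcome, and q the chance that a recurrer who drops out recurs first. Then

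rate = 0.65(1 − d) / [0.65(1 − d) + 0.35(1 − d + dq)].

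With d = 0.20 the numerator is 0.52. For recurrences uniform over Days 91-360:

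| Dropout uniform over | q | Observed failures | Rate |
|---|---|---|---|
| Days 0-360 | 134.5/360 = 0.374 | 0.35 × 0.875 = 0.306 | 62.9% |
| Days 91-360 | 0.5 | 0.35 × 0.900 = 0.315 | 62.3% |
| Days 180-360 | 179/269 = 0.665 | 0.35 × 0.933 = 0.327 | 61.4% |

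Simulation agrees (63.0%, 62.2%, 61.5%). With recurrences concentrated early it gives 62.2% for dropout over the whole year and 60.7% for late dropout. The range is therefore about 61-63%, or 2 to 4 points low.

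With d = 0.10, dropout over Days 0-360 gives 0.585/(0.585 + 0.328) = 64.1%, and over Days 91-360 gives 0.585/(0.585 + 0.3325) = 63.8%. Both are about 1 point low.

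**3. Alternative reading: everyone who left is deleted, including those who had recurred.** With dropout unrelated to outcome, rate = 0.65(1 − d)/(1 − d) = 65.0%, which is unbiased. Kaplan-Meier also gives 65.0% here.

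**4. Both readings on the same data when leaving depends on outcome.** Assume 40% of recurrers leave after recurring and 10% of the others leave. Total dropout is 0.35 × 0.40 + 0.65 × 0.10 = 20.5%.

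- Natural reading: 0.585/(0.585 + 0.35) = 62.6%.
- Alternative reading: 0.585/(0.585 + 0.21) = 73.6%.
- Kaplan-Meier, simulated with dropout among non-recurrers uniform over Days 0-360: 63.4%.
- Main analysis: 0.65 × 0.90 = 58.5%.

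With milder dependence at 20% dropout, where recurrers are 2 or 3 times as likely to leave, the alternative reading gives 69.2% or 71.7%.

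**5. Effect on the decision.** Every deleted subject is already a failure in the main analysis, so deletion leaves the successes unchanged and shrinks the denominator. The rate and its lower bound can only rise. The smallest main pass at 188 is 108/188 = 57.4% (lower bound 50.04%); deleting 38 gives 108/150 = 72.0% (lower bound 64.1%). In the other direction, 104/200 = 52.0% (lower bound 44.8%) misses the goal, while 104/160 = 65.0% (lower bound 57.1%) clears it.

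**The case against.** The strongest reply is that little depends on this. Counting missing as failure is already the worst case for loss to follow-up against a fixed goal, so a positive main result needs no harsher test. The bias under the natural reading is small and downward. At N = 200 with expected counts, 104 successes among roughly 165 to 171 analysed subjects give exact lower bounds of 55.2% and 53.1%, both still above 50%. An approximate recurrence-free rate could be read from the planned curve, and the programming specifications and mock tables, which are separate documents, may settle the wording. All of this stands, and it limits the point to the quality of one estimate.

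Three stronger readings are tempting.

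- **That the sentence yields anything from about 61% to 74%.** This sets the natural reading under outcome-independent dropout beside the alternative reading under assumed outcome-dependent dropout. With independent dropout the two readings span about 61% to 65%. The wider gap in step 4 rests on leaving rates that the documents do not give.
- **That the SAP intends to delete known failures.** An endpoint treated as missing does not describe a recorded recurrence, and the same section requires acute failures and late repeat ablations to be counted as failures within the analysis population. The wording leaves deletion open but does not favour it.
- **That the sensitivity analysis is useless because it cannot overturn a positive result.** Nor could the Kaplan-Meier rate: if event-free completers are followed to the evaluation day, it cannot fall below successes divided by N. After a negative result, deletion does show how much the missing-as-failure rule contributed.

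**Conclusion.** The point holds as a defect in the sensitivity estimate of the 12-month rate. Followed as naturally read, the deletion rule gives about 61-63% when the truth is 65% at the planned 20% dropout, and is about 1 point low at 10%. This assumes recurrences spread over Days 91-360 and dropout unrelated to outcome. The sentence also leaves open a second analysis that is unbiased under independent leaving and biased upward if recurrers leave more often; 73.6% against 62.6% illustrates this under assumed leaving rates.

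It does not touch the superiority decision or false-positive control. A better estimate is available from data the trial already collects, so the change is worth making even though the bias is modest.

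**What to change.** 1. State in SAP 6.5.1 that a primary failure observed before a subject leaves remains a failure in every analysis.
2. Beside the deletion analysis, report the Kaplan-Meier estimate of freedom from primary failure at 12 months with a 95% confidence interval (Greenwood variance, log-log scale).
3. Define the event for that estimate as the full primary failure: symptomatic AF/AT/AFL after blanking, repeat ablation after blanking, and acute procedural failure as a Day 0 event.
4. State how ITT subjects without an index ablation are handled. SAP 6.2.1 can include them, and they have no Day 0.
5. Count event-free subjects who complete the 12-month visit within its Day 330-420 window as followed to 12 months. Otherwise those seen on Days 330-360 would be censored before the Day 361 end of the planned curve.

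The cost is SAP wording and one redefined event, with no new data. The downside is that Kaplan-Meier assumes non-informative censoring. In step 4, where that fails, it was 1.6 points low, and the missing-as-failure main analysis remains the lower bound.
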